1 BACKGROUND

Peptic ulcer disease is a chronic inflammatory condition of the stomach and duodenum. Despite the fact that the disease has relatively low mortality, it results in substantial suffering of those affected.

A strong association between *H. pylori*, chronic superficial gastritis and gastrointestinal disease has been well established. *H. pylori* is associated with type B gastritis, duodenal ulcer, gastric ulcer, gastric cancer, and non-Hodgkin's lymphoma.

H. pylori was first cultured successfully from human gastric mucosa in 1982. The organisms, spiral gram negative bacteria, are found in the human stomach between the gastric epithelium and the mucosa. Isolates implicated in the above mentioned diseased states are distinguished by the production of copious amounts of endogenous urea amidohydrolase (urease). The enzyme catalyzes the breakdown of urea to carbon dioxide and ammonia, which are absorbed into the bloodstream.

Methods available for detecting current infection of the human stomach by *H. pylori* are generally divided into two general types: Invasive and Non-invasive. Invasive methods are so called because they include, as a first step, an esophagogastroduodenoscopy ("EGD") with collection of gastric biopsies. These biopsies are then examined by one or more detection methods: histological examination of stained tissue, microbiological culture of the organism, or direct detection of urease activity in the tissue (for example, the CLOtest®). Biopsy based methods are expensive, entail some patient risk and discomfort, and may give false negative results due to sampling errors when colonization of the gastric mucosa is patchy.

The C13 Urea Breath Test kit is intended for use with the ARJ Breath Test Analyzer, which is a combined product referred to as the ARJ C13 Breath Test System for the qualitative detection of urease associated with *Helicobacter pylori* as an aid in detecting *H. pylori*.

2 STUDY RATIONALE

Gastritis describes a group of conditions with one thing in common: inflammation of the lining of the stomach. The inflammation of gastritis is most often the result of infection with the same bacterium that causes most stomach ulcers. Injury, regular use of certain pain relievers and drinking too much alcohol also can contribute to gastritis. *Helicobacter pylori* (*H. pylori*): A bacteria that lives in the mucous lining of the stomach; without treatment, the infection can lead to ulcers, and in some people, stomach cancer.

Patients who are experiencing the affects of gastritis, which is an inflammation, irritation, or erosion of the lining of the stomach require an identification of the status and generation of urease in the stomach to provide a definitive diagnosis.

By ingesting a low dosage of C13 urea, the patients' exhaled breath is then measured to record the level of change of ¹³C labeled urea detectable in a patient's breath. This is measured before and after the ingestion of the urea mixture. The exhaled breath is read by the analyzer which provides an immediate diagnoses and is non-invasive. Although other C13 Urea Test Kits and analyzers are in the market, the ARJ C13 Breath Test System is believed to be equivalent in functionality and will be manufactured in the U.S. which can provide and cost effective equivalent product.

2.1 Risk Benefit Assessment

2.1.1 Risk

- For in vitro diagnostic use only. The 13C-urea powder and Citric Powder are dissolved in a glass of water and the resulting solution is taken orally as part of the diagnostic procedure. In the case of accidental overdose – drink water and call the physician.
- A negative result does not rule out the possibility of *H. pylori* infection. False negative results can occur with this procedure. If clinical signs suggest *H. pylori* infection, retest with a new sample or an alternate method.
- A false positive test may (rarely) occur due to urease associated with other gastric spiral organisms observed in humans such as *Helicobacter heilmanni*.
- A false positive test could occur in patients who have achlorhydria.

2.1.2 Benefit

- Noninvasive diagnosis of H. pylori.
- High degree of testing accuracy.

3 STUDY OBJECTIVES

3.1 Primary Objective

The primary objective is to assess the clinical efficacy of the ARJ C13 Breath Test System as compared to the ARJ Pylo Plus test which tests the Study Subject's biopsy to determine the Study Subject's level of H.pylori. The results of the testing of C13 urea presence in the Study Subjects' breath and read via the breath analyzers is compared to the results of the ARJ Pylo Plus test per study subject.

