| RATIONALE | 
Patients who are experiencing the effects of gastritis, which is an inflammation, irritation, or erosion of the lining of the stomach require an identification of the status and generation of urease in the stomach to provide a definitive diagnosis. Historically, this has been achieved via an upper endoscopy, where a thin tube containing a tiny camera, is inserted through your mouth and down into your stomach to look at the stomach lining. The doctor will check for inflammation and may perform a biopsy, a procedure in which a tiny sample of tissue is removed and then sent to a laboratory for analysis.
 
By ingesting a low dosage of C13 urea, the patients' exhaled breath is then measured to record the level of change of ^{13}C labeled urea detectable in a patient's breath. This is measured before and after the ingestion of the urea mixture. The exhaled breath is read by the analyzer which provides an immediate diagnoses and is non-invasive. Although other C13 Urea Test Kits and analyzers are in the market, the ARJ C13 Breath Test System is believed to be equivalent in functionality and will be manufactured in the U.S. which can provide a cost effective equivalent product.
 |
| STUDY DESIGN | Up to 3 centers, non-randomized, comparative study to compare the ARJ C13 Urea Breath Test System to the ARJ Pylo Plus rapid urease test. |
| PRIMARY OBJECTIVE | To demonstrate the ARJ C13 Breath Test System equivalency to the predicate ARJ Pylo Plus rapid urease test. |
| SECONDARY OBJECTIVES | None |
| NUMBER OF SUBJECTS | Test Group: Approximately 100 - 300 Study Subjects |
| SUBJECT SELECTION CRITERIA | 
Inclusion Criteria:
 
 • Male or Female \geq 18 years of age • Patients who are experiencing the effects of gastritis • Written informed consent (and assent when applicable) obtained from subject and ability for subject to comply with the requirements of the study. 
Exclusion Criteria:
 
 • Pregnant or lactating female • Study Subjects currently taking antibiotics • Presence of a condition or abnormality that in the opinion of the Investigator would compromise the safety of the patient or the quality of the data • Fasting required one hour prior to testing • Study Subjects shall not consume the following items prior to the test 
 ○ Mouthwash |

| | |

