|----------------------------------------------------------------|----------------------------------------------------------------------------------------------------------------------------------------------------------------------------------------------------------------------------------------------------------------------------------------------------------------------------------------------------|
| | 
  Chewing gum  Carbonated beverages  Cigarette smoke  Acetone (to simulate the effect of ketone production that may result from some diets)  Alcohol |
| TEST PRODUCT, DOSE, AND ROUTE OF ADMINISTRATION | ARJ C13 Breath Test System will be administered one time during a one-time visit per Study Subject, according to the standard procedure described in the device's instructions. The administration shall be done orally followed by a series of specifically timed exhalations of the subject's breath. |
| CONTROL PRODUCT, DOSE AND ROUTE OF ADMINISTRATION | The ARJ Pylo Plus comparator product will be administered once at a follow-up appointment where the ARJ Pylo Plus test will be administered by the physician using a biopsy from the patient to test the presence of h. Pylori. |
| DURATION OF SUBJECT PARTICIPATION AND DURATION OF STUDY | 
Subjects will be on study for 2 days
 
Screening: up to 90 days
 
Test: 2 days
 
Reporting: 30 days
 
The total duration of the study is estimated to be 120 days. 3 months for subject screening and testing 1 month for final analysis and reporting.
 |
| CONCOMITANT MEDICATIONS | 
Allowed:
 
 • No exclusions with the requirement of fasting one hour prior to testing 
Prohibited:
 
 • Antibiotics |
| EFFICACY EVALUATIONS | The efficacy evaluations shall compare, per study subject, the results of the ARJ C13 Breath Test System to the results of the proven ARJ Pylo Plus test and the biopsy histology, rapid urease and culture tests. |
| PRIMARY ENDPOINT | 
 • Results of the test study patients' breath tests demonstrate acceptance criterion of $\geq 95\%$ to the ARJ Pylo Plus test readings. |
| SECONDARY ENDPOINTS | None |
| OTHER EVALUATIONS | None |

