4 STUDY DESIGN

4.1 Study Overview

This will be up to three sites, open label, comparative trial. Approximately 100 – 300 (number) of subjects are planned. Each subject will be administered a single dose of study drug one time during a single visit. Evaluations will be taken at baseline and at a specified time during the testing session.

Screening data will be reviewed to determine subject eligibility. Upon patient's consent, subjects who meet all inclusion criteria and none of the exclusion criteria will be entered into the study.

The following testing regimens will be used:

- Using three independent sites, a total of 100-300 clinical samples are to be obtained from a population of symptomatic individuals who have been prescribed endoscopic examination for the detection of H.Pylori infection. The physician(s) will schedule test subjects per standard of care for an endoscopy procedure in which a gastric mucosal biopsy will be obtained. In addition to the physician's standard testing, the obtained tissue will also be used to perform the following tests:
 - Histology
 - Rapid Urease Test
 - Culture
- Experimental treatment ARJ C13 Urea Test dosage shall be a one-time dosage at time of initial testing.
- Comparator – ARJ Pylo Plus shall be a one-time test performed during a follow-up visit to examine the study subject's biopsy to determine the level of urease presence.
- Total duration of subject participation will be two visits. Total duration of the study is expected to be 4 months.

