5 CRITERIA FOR EVALUATION

5.1 Primary Efficacy Endpoint

Upon the completion of the four (4) months of testing, the test results of ARJ C13 Urea are expected to demonstrate equivalency to the ARJ Pylo Plus test results and equivalency to the results of the histology, rapid urease and culture tests results.

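### The only numeric success criterion is 95% agreement with Pylo Plus, a biopsy urease test that can itself miss infection, and no infection status is defined to show which test erred

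*Combined protocol and SAP*

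**What the plan says.** **Pylo Plus alone.** The synopsis primary objective is to show "equivalency to the predicate ARJ Pylo Plus rapid urease test". The synopsis primary endpoint is that the breath tests "demonstrate acceptance criterion of $\geq 95\%$ to the ARJ Pylo Plus test readings". Section 3.1 says the breath results are "compared to the results of the ARJ Pylo Plus test per study subject".

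**Pylo Plus and other references.** Section 5.1, the primary efficacy endpoint, adds "equivalency to the results of the histology, rapid urease and culture tests results". The synopsis row on efficacy evaluations compares the breath test with "the results of the proven ARJ Pylo Plus test and the biopsy histology, rapid urease and culture tests", and the synopsis primary analysis plan repeats these per-subject comparisons. None of these places gives a percentage or margin for the added tests, a way to combine them, or a rule for conflicting results.

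**What the tests measure.** Section 4.1 describes Pylo Plus as used "to examine the study subject's biopsy to determine the level of urease presence". Section 1 describes the breath test as a qualitative test for urease linked to *H. pylori*, used as an aid in detecting the organism.

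**Known errors.** Section 1 lists histology, culture and direct urease detection as biopsy methods and says that such methods "may give false negative results due to sampling errors when colonization of the gastric mucosa is patchy". Section 2.1.1 says of the breath test: "A false positive test may (rarely) occur due to urease associated with other gastric spiral organisms observed in humans".

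Section 14 leaves the detailed SAP to be written later.

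**The concern.** The 95% rule uses one fallible test as the yardstick. This matters in two ways.

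- **Correct positives penalised.** If an infected subject's biopsy misses the organism, Pylo Plus reads negative. A positive breath test in that subject is right but is scored as a disagreement.
- **Common errors rewarded.** Both tests detect urease. If the conclusion rests on Pylo Plus alone, any subject whom both tests misclassify in the same direction is scored as an agreement.

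The device is intended to help detect *H. pylori*. Agreement with a single imperfect urease test does not show which test was wrong when they differ, or whether either was right when they agree. The trial could fail an accurate device or pass one that shares its comparator's errors. Histology and culture do not depend on urease and are already planned, but the plan never uses them to settle the question.

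**Working it through.** **The plan's own figure.** The sample size of 100 to 300 cannot be reproduced. Section 14.4 justifies it by analogy with studies of 100 and 79 subjects. The documents give no significance level, power, expected agreement, margin or prevalence.

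**Inputs from the documents.** The 95% threshold is in the synopsis primary endpoint, and n = 100 to 300 is in the synopsis and Section 14.4.

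**Assumptions.** The synopsis does not say which measure the 95% refers to, or whether a confidence limit must clear it. I read it as observed overall agreement of at least 95%. Prevalence (20% to 50%), Pylo Plus sensitivity (85% to 95%) and Pylo Plus specificity (100%, with one case at 98%) are assumed.

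**Step 1: expected agreement of a breath test that is always right.**

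agreement = prevalence × sensitivity + (1 − prevalence) × specificity, with sensitivity and specificity those of Pylo Plus.

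For prevalence 40%, sensitivity 85%, specificity 100%: 0.40 × 0.85 + 0.60 × 1 = 0.940.

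With specificity 100%, this falls below 95% only when prevalence × (1 − sensitivity) exceeds 5%.

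**Step 2: chance of passing.** This is the exact binomial probability of at least 95 agreements in 100, or 285 in 300.

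| Prevalence | Pylo Plus sensitivity | Pylo Plus specificity | Expected agreement | Pass, n=100 | Pass, n=300 |
|---|---|---|---|---|---|
| 20% | 90% | 100% | 98.0% | 98.5% | about 100% |
| 30% | 95% | 100% | 98.5% | 99.6% | about 100% |
| 40% | 85% | 100% | 94.0% | 44% | 28% |
| 40% | 90% | 98% | 94.8% | 58% | 51% |
| 50% | 85% | 100% | 92.5% | 23% | 5.6% |

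When expected agreement is below 95%, the larger trial passes less often.

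**Step 3: errors common to both tests, as a limiting case.** Take prevalence 50%, sensitivity 85% for both tests, specificity 100%, and the same infected subjects missed by both. Agreement is 100%, so the 95% rule is always met. True accuracy is 0.50 × 0.85 + 0.50 = 92.5%. Judged against the truth, the same test would reach 95% with chance 23% at n=100 and 5.6% at n=300. The documents do not say how far the two tests' errors overlap.

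**Step 4: precision of a paired comparison.** Assume 40% prevalence and that the two tests disagree in 10% of infected subjects. With a true difference near zero, the 95% half-width for the difference in sensitivity is about 1.96 × √(0.10 / number infected).

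- n=100, 40 infected: 1.96 × √(0.10/40) = 9.8 percentage points.
- n=300, 120 infected: 1.96 × √(0.10/120) = 5.7 percentage points.

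**The case against.** **The plan does not rely on Pylo Plus alone.** A reader might infer from the synopsis and Section 3.1 that success is judged only by Pylo Plus. Section 5.1 does not support that, because it puts histology, rapid urease and culture into the primary efficacy endpoint. Under that wording, a false positive common to both urease tests would appear as disagreement with histology and culture. This part of the objection stands: common errors pass unnoticed only under the Pylo Plus-alone reading. Section 5.1 still gives no criterion for the added tests and no way to decide who is infected.

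**Equivalence to a predicate is the stated question, and agreement measures it directly.** This also stands, and is why the agreement criterion should be kept. Replacing it with paired accuracy differences would need a margin and a sample-size basis that the plan lacks.

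**Some steps are inference.** Section 1 speaks of biopsy methods as a class, gives no rate and does not name Pylo Plus, though it includes direct urease detection. Section 2.1.1 describes the spiral-organism error for the breath test only and calls it rare. That it also affects Pylo Plus is inferred from the shared urease principle. The false-negative argument does not need that inference.

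**Histology and culture are biopsy methods too.** The sampling error in Section 1 applies to them, so a correct breath positive can still be scored as wrong. This limits the remedy.

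**Conclusion.** The concern holds in a limited form. The only numeric criterion is against a biopsy urease test that belongs to a class the protocol says can miss infection. The further comparisons in Section 5.1 and the synopsis have no criterion and no definition of infection status. The 95% result therefore cannot separate a breath-test error from a Pylo Plus error.

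The direction is clear but the size is not. Across the assumed rates, a breath test that is always right passes almost always or as rarely as 5.6% of the time. These figures rest on reading the rule as observed overall agreement and on prevalence and Pylo Plus accuracy that the documents do not give.

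A reader might infer that an accurate test is bound to fail once expected agreement is below 95%. That does not follow: at 94.8% it still passes with chance 58% at n=100 and 51% at n=300. The documents also do not support saying that failure is likely, since they give no error rate for Pylo Plus.

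**What to change.** 1. Keep the Pylo Plus agreement table and the 95% criterion.
2. Before results are seen, define infection status for every subject, not only discordant pairs, from the planned histology and culture. Status is positive if either is positive, negative if both are negative, and indeterminate if culture is missing or failed and histology is negative. Leave Pylo Plus and the listed rapid urease test out of this definition.
3. Report sensitivity and specificity of both the breath test and Pylo Plus against that status, with the paired differences and 95% intervals. Prespecify this as the analysis used to interpret the agreement result.
4. Reconcile the synopsis objective, the synopsis primary endpoint and Section 3.1 with Section 5.1 on which references the primary conclusion uses.

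**Cost.** Protocol and SAP wording and a set of paired tables; no new procedure, because Section 4.1 already plans histology and culture. Some subjects will be indeterminate. The intervals will be wide, about ±10 points for the sensitivity difference at n=100 and ±6 at n=300 under the assumptions above. Histology and culture share biopsy sampling error, so the problem is reduced, not removed.

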3.2 Secondary Objectives

None

4 STUDY DESIGN

4.1 Study Overview

This will be up to three sites, open label, comparative trial. Approximately 100 – 300 (number) of subjects are planned. Each subject will be administered a single dose of study drug one time during a single visit. Evaluations will be taken at baseline and at a specified time during the testing session.

Screening data will be reviewed to determine subject eligibility. Upon patient's consent, subjects who meet all inclusion criteria and none of the exclusion criteria will be entered into the study.

The following testing regimens will be used:

- Using three independent sites, a total of 100-300 clinical samples are to be obtained from a population of symptomatic individuals who have been prescribed endoscopic examination for the detection of H.Pylori infection. The physician(s) will schedule test subjects per standard of care for an endoscopy procedure in which a gastric mucosal biopsy will be obtained. In addition to the physician's standard testing, the obtained tissue will also be used to perform the following tests:
 - Histology
 - Rapid Urease Test
 - Culture
- Experimental treatment ARJ C13 Urea Test dosage shall be a one-time dosage at time of initial testing.
- Comparator – ARJ Pylo Plus shall be a one-time test performed during a follow-up visit to examine the study subject's biopsy to determine the level of urease presence.
- Total duration of subject participation will be two visits. Total duration of the study is expected to be 4 months.

5 CRITERIA FOR EVALUATION

5.1 Primary Efficacy Endpoint

Upon the completion of the four (4) months of testing, the test results of ARJ C13 Urea are expected to demonstrate equivalency to the ARJ Pylo Plus test results and equivalency to the results of the histology, rapid urease and culture tests results.

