| 15.4 Publications..... | 21 |
| 15.5 Investigator Responsibilities | 21 |

LIST OF ABBREVIATIONS

| | |
|--------------|-------------------------------------------------------------|
| AE | Adverse Event |
| CFR | Code of Federal Regulations |
| CRF | Case Report Form |
| DMC | Data Monitoring Committee |
| DSMB | Data Safety Monitoring Board |
| FDA | Food and Drug Administration |
| GCP | Good Clinical Practice |
| HIPAA | Health Insurance Portability and Accountability Act of 1996 |
| ICF | Informed Consent Form |
| ICH | International Conference on Harmonisation |
| IEC | Independent Ethics Committee |
| IRB | Institutional Review Board |
| PI | Principal Investigator |
| SAE | Serious Adverse Experience |

PROTOCOL SYNOPSIS

| | |
|-----------------------------------|----------------------------------------------------------------------------------------------------------------------------------------------------------------------------------------------------------------------------------------------------------------------------------------------------------------------------------------------------------------------------------------------------------------------------------------------------------------------------------------------------------------------------------------------------------------------------------------------------------------------------------------------------------------------------------------------------------------------------------------------------------------------------------------------------------------------------------------------------------------------------------------------------------------------------------------------------------------------------------------------------------------------------------------------------------------------------------------------------------------------------------------------------------------------------------------------------------------------------------------------------------------------|
| TITLE | ARJ C13 Urea Breath Test: An Open-Label, Comparator Group Study to Evaluate the equivalency of the ARJ C13 Urea Breath Test System to the predicate device ARJ Pylo Plus. |
| SPONSOR | ARJ Medical, Inc. |
| FUNDING ORGANIZATION | Gulf Coast Medical |
| NUMBER OF SITES | 3 |

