| STATISTICS Primary Analysis Plan | Each review of the subject(s) shall be recorded including documentation of status at selection and again during the comparative study test visit. The baseline reading and each subsequent breath test shall provide a complete series of breath readings per Study Subject. The analyzed breath readings shall be documented. The analysis of the results shall be graphed for the Study Group. This is to illustrate progression from start of the testing through the most recent day's tests of the study. At the end of the study, the results of the Study Group's ARJ C13 Breath Test System shall be compared to the results of the ARJ Pylo Plus, histology, rapid urease and culture results as compared per study subject. The Study Group's results shall be calculated and compared for equivalency. Adverse Events shall be documented by subject. All identified Adverse Events shall be given a level of adversity per Table 3- AE Severity Grading. The analysis of the results shall be graphed per subject and overall of all subjects per study group. This is to illustrate adversity from start of testing through the most recent testing per study group. |
| Rationale for Number of Subjects | The clinical studies for the ARJ C13 Urea Breath Test predicate device Pylo-Plus (K052708) included 100 study subjects. The recent clearance (May 2013) of the Exalenz Bioscience Ltd. Breath ID Hp System (K130524) included 79 pre-treatment study subjects. The rationale to use approximately 100 - 300 study subjects shows equivalency to the two (2) related clinical studies. |

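### The primary endpoint exists in a narrower version (Pylo Plus alone) and a wider one (Pylo Plus plus histology, rapid urease and culture), and nothing says which governs.

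*Combined protocol and SAP*

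**What the plan says.** **Pylo Plus alone.** The title in the synopsis describes a study "to Evaluate the equivalency of the ARJ C13 Urea Breath Test System to the predicate device ARJ Pylo Plus". The synopsis primary objective is "To demonstrate the ARJ C13 Breath Test System equivalency to the predicate ARJ Pylo Plus rapid urease test". The synopsis primary endpoint sets an acceptance criterion of at least 95% relative "to the ARJ Pylo Plus test readings". In Section 3.1 the breath result "is compared to the results of the ARJ Pylo Plus test per study subject". Pylo Plus is also the only test labelled as the comparator, in the synopsis control-product row ("The ARJ Pylo Plus comparator product will be administered once at a follow-up appointment") and in Section 4.1.

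**Pylo Plus and other tests.** Section 5.1, Primary Efficacy Endpoint, says that the breath test results "are expected to demonstrate equivalency to the ARJ Pylo Plus test results and equivalency to the results of the histology, rapid urease and culture" tests. The synopsis efficacy evaluations compare the breath test "to the results of the proven ARJ Pylo Plus test and the biopsy histology, rapid urease and culture tests". In the synopsis primary analysis plan the end-of-study results "shall be compared to the results of the ARJ Pylo Plus, histology, rapid urease and culture results as compared per study subject".

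**Lower levels.** Secondary objectives are given as none in the synopsis and in Section 3.2. The synopsis rows for secondary endpoints and other evaluations are also none. Section 5.2, headed Secondary Efficacy Endpoints, deals only with adverse conditions.

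**The concern.** A confirmatory study needs one statement of what counts as success. Here two are in force. The first has a number and one reference. The second carries the formal endpoint heading and has more references, but it has no number and does not say whether every comparison must succeed. The added tests cannot be read as secondary or exploratory, because the protocol declares those levels empty.

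At stake is the verdict of the study: a result at or above 95% against Pylo Plus settles the question under the synopsis and leaves it open under Section 5.1.

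Timing adds to this. Section 14 requires the detailed SAP only before the final data are analysed. The synopsis starts analysis of study results when 20% of subjects have been tested and repeats it monthly; Section 14.3 starts it after two weeks. Neither excludes comparative results. The version could therefore be chosen after results have been seen.

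**Working it through.** The protocol has no figure to reproduce on this point: it gives no expected agreement, margin, alpha or power, and the 100 to 300 subjects rest on the sizes of two earlier studies (100 and 79). The check is first textual, then illustrative.

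**Step 1. The passages side by side**

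| Place | References named | Criterion |
|---|---|---|
| Synopsis title | Pylo Plus | none |
| Synopsis primary objective | Pylo Plus | none |
| Synopsis primary endpoint | Pylo Plus | at least 95% |
| Section 3.1 | Pylo Plus | none |
| Section 5.1 | Pylo Plus, histology, rapid urease, culture | none |
| Synopsis efficacy evaluations | all of these | none |
| Synopsis primary analysis plan | all of these | none |

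The split is not simply synopsis against body: the synopsis is divided within itself. No entry ranks the references or gives one statement precedence.

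**Step 2. Can the same data give different verdicts?** Only if some criterion applies to the added tests. Assume that 95% observed agreement is required of each. Then 96/100 against Pylo Plus with 90/100 against culture passes the narrower version and fails the wider one.

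**Step 3. How often, under stated assumptions.** None of these inputs is in the protocol except the 95% and the range of N: true agreement with Pylo Plus is 98%; 95% is read as an observed proportion; the same 95% is required of every reference. Passing means at least 95 of 100, or at least 285 of 300. The exact binomial probability of passing is:

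| True agreement | N = 100 | N = 300 |
|---|---|---|
| 98% (call it a) | 0.9845 | 0.9996 |
| 95% (call it b) | 0.6160 | 0.5681 |

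For independent comparisons, the chance of passing on Pylo Plus but failing Section 5.1 is a × (1 − product of the pass probabilities of the other references). If the disagreements with Pylo Plus are all contained in those with one weaker reference, it is a − b. At N = 100:

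- One composite biopsy reference at 98%: 0.9845 × (1 − 0.9845) = 0.015.
- Three references at 98%: 0.9845 × (1 − 0.9845³) = 0.045.
- One reference at 95%, two at 98%: 0.9845 × (1 − 0.6160 × 0.9845²) = 0.397.
- One composite at 95%: 0.9845 × (1 − 0.6160) = 0.378.
- One reference at 95%, disagreements fully shared: 0.9845 − 0.6160 = 0.369.

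At N = 300, three references at 98% give 0.001. One at 95% with two at 98% gives 0.432, and the fully shared case gives 0.9996 − 0.5681 = 0.4315, so about 43% either way.

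**The case against.** The strongest reply is that the two statements do not exclude each other. Section 5.1 contains the Pylo Plus comparison and adds to it, so one data set can satisfy both. This stands: the versions are narrower and wider. A reader might infer that they are incompatible, but the text does not support that.

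A related reply is that only one numerical rule exists. Section 5.1 speaks of an expectation and sets no threshold, so a numerical pass/fail conflict appears only when 95% is extended to the other tests. This also stands, and it is why Step 3 is only an illustration. It does not remove the problem, because an endpoint that requires equivalency to further tests with no criterion cannot be judged as met or not met.

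Third, the weight of the text favours Pylo Plus: title, objective, numerical endpoint and comparator label all point to it, and Section 4.1 introduces the other tests as further uses of the biopsy tissue. That is good reason to choose the narrower version. It does not give it precedence over the section headed Primary Efficacy Endpoint.

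Two stronger readings are tempting. One is that the versions would usually disagree. That needs all three added references to agree at only 95% and the comparisons to be independent. Independence is implausible, because one breath result is compared with tests on the same subject's biopsy, and nothing in the protocol supports the 95% rates. The other is that the sponsor means to pick the version afterwards. Nothing shows this: the analysis plan places the full comparison at study end, the stated interim purpose is to follow study progression, and a SAP is required before the final analysis. The documents leave the possibility open and no more.

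**Conclusion.** The primary endpoint is wrong as written. This is an internal inconsistency: a narrower and a wider version are both in force, only the narrower has a criterion, and no ranking or lower level accommodates the added tests. That conclusion rests on the text alone and needs no assumption.

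Its practical size is not known. Under the assumptions in the working, at N = 100 the gap is small (about 1.5% to 4.5%) when every reference agrees at 98%, and substantial (about 37% to 40%) when one agrees at 95%. The second range changes little with the dependence assumption or with a single composite in place of three tests. Other agreement rates would give other figures.

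Two neighbouring questions are separate and do not bear on this conclusion: whether 95% is an observed proportion or a confidence bound, and whether rapid urease in Section 5.1 is a different test from Pylo Plus, which the synopsis itself calls a rapid urease test.

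**What to change.** Before any comparative result is analysed, state one primary endpoint in the same terms in the synopsis (objective, endpoint, efficacy evaluations, analysis plan), Section 3.1 and Section 5.1.

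- **Narrower version.** Agreement with Pylo Plus at the stated 95% or more fits the title, the objective and the comparator label. Amend Section 5.1 to say so, name histology, rapid urease and culture as supportive in the efficacy evaluations and analysis plan, and enter them in the synopsis row for other evaluations, now none. This costs wording only: the tests and comparisons are already planned.
- **Wider version.** If Section 5.1 is what is meant, give the criterion for each added reference, or for one composite biopsy reference with its definition, and say whether all must be met. Bring the objective and the synopsis endpoint into line. This adds success criteria and lowers the chance of success, so the planned number of subjects should be looked at again.

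The wording-only cost assumes that 95% stays an observed proportion. Read as an exact two-sided 95% lower confidence bound, it would need 100/100 agreement at N = 100, which should be decided separately.
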